3.7 Toxicity Management Guidelines

All AEs should be assessed using NCI-CTCAE v5.0 criteria. CRS will be graded per the ASTCT Consensus Grading Criteria for CRS (described in Section 3.7.1.2). Ocular AEs for MIRV will be graded per the tables in Appendix Section 16.6. These guidelines are not meant to be prescriptive, and investigators should always use clinical judgement. Investigators should always err on the side of caution if treatment-related toxicity is suspected. Subjects should be thoroughly evaluated to rule out any alternative etiology (e.g., disease progression, concomitant medications, and infections). In the absence of a clear alternative etiology, the possibility of an immune-related AE should be considered.

Every effort should be made to administer study treatment on the planned dose and schedule. If PLD or MIRV dosing is delayed, SL-172154 should also be delayed so that the dosing interval between PLD or MIRV and SL-172154 can be preserved. This will result in the cycle being delayed. If an SL-172154 dose is not given, the dose should be considered skipped, and the cycle should not be delayed. Please consult with the Medical Monitor if further guidance is needed.

3.7.1 Toxicity Management Guidelines for SL-172154

The toxicity management guidelines provided in this section represent general guidance for AEs that are considered by the investigator to be possibly related or related to treatment with SL-172154.

Table 3 describes the dose levels to be used for dose reductions due to AEs that are considered by the investigator to be possibly related or related to treatment with SL-172154. Only one level dose reduction is permitted for AE management and then SL-172154 administration should be held. Investigators always have the option to perform a more conservative dose modification if clinically indicated (i.e., dose interruption as opposed to dose reduction). Any AE deemed to be related to SL-172154 that requires a dose hold of more than 28 days will result in permanent discontinuation of SL-172154.

Table 3 SL-172154 Dose Levels for Dose Reductions

Starting SL-172154 Dose Level (mg/kg)	Dose Level Reduction (mg/kg)
1.0	Interrupt SL-172154 until toxicity resolves to ≤ Grade 1 or baseline and then restart at same dose level or discontinue. Reduction of SL-172154 below 1.0 mg/kg will not be permitted.
3.0	1.0 mg/kg
6.0	3.0 mg/kg

3.7.1.1 Management of Infusion-Related Reactions [SL-172154]

General Guidance for Infusion-Related Reactions (IRRs) [Rosello, 2017a]

IRRs have been temporally related to SL-172154 administration. Subjects must be closely monitored for signs and symptoms of IRRs with prompt institution of treatment. Appropriate drugs and medical equipment to treat hypersensitivity reactions (HSRs), IRRs, and CRS must be immediately available, and study personnel must be trained to recognize and treat these toxicities. Premedication for IRR prophylaxis with dexamethasone (8 mg IV), an antipyretic and antihistamines should be administered at least 30 minutes prior to each SL-172154 administration as outlined in Section 5.1.1. Additional premedication with dexamethasone one day prior to SL-172154 infusion is not required but can be optionally given. The dose and administration method of prophylactic premedication can be modified at the Investigator's discretion. Subjects should be notified that symptoms may occur during the first infusion and for up to several hours afterwards or with subsequent infusions. In the SL03-OHD-101 study, IRRs occurred during the infusion or within 2 hours after the end of infusion. Instruct subjects to contact their physician if symptoms or signs of an IRR occur. If **IRR events** occur, ad hoc labs should be collected as noted in Section 6.5.9.1.

Severity	Management
Grade 1	
• Infusion interruption not indicated.• Vital signs should be measured after the onset of an IRR approximately every 15 minutes through the completion of the infusion followed by approximately every 15 minutes for one hour after completion of the SL-172154 infusion and then approximately every 30 minutes for the second hour after completion of the SL-172154 infusion.• Monitor subjects with close observation in an outpatient or inpatient setting until recovery from symptoms
Grade 2	
• Temporarily interrupt SL-172154.• Vital signs should be measured after the onset of an IRR approximately every 15 minutes through the completion of the infusion followed by approximately every 15 minutes for one hour after completion of the SL-172154 infusion and then approximately every 30 minutes for the second hour after the completion of the SL-172154 infusion.• Begin IV infusion of normal saline and treat symptoms as indicated and per institutional guidelines, e.g., with antipyretic and antihistamines; consider opioids (e.g., meperidine) for rigors, leukotriene inhibitor, bronchodilator therapy, or corticosteroids as appropriate.• Monitor subjects with close observation in an outpatient or inpatient setting until recovery from symptoms. Consider if admission to hospital is necessary.

General Guidance for Infusion-Related Reactions (IRRs) [Rosello, 2017a]	
	
• Restart the infusion after resolution of symptoms. Based on the severity of symptoms, reduce the rate to $\leq 50\%$ of the rate at which the reaction occurred.• If symptoms recur, then no further SL-172154 will be administered at this visit.• Subsequent Infusions:
◦ If the Grade 2 IRR signs and symptoms were not severe, the investigator may administer the next two infusions at the current dose but at $\leq 50\%$ rate. If the symptoms do not recur, the infusion rate may be increased back to the original rate stated in the protocol.◦ If the Grade 2 IRR signs and symptoms were severe, the investigator may reduce the SL-172154 dose for the next two infusions to 1 mg/kg. If the symptoms do not recur, SL-172154 dose may be increased back to 3 mg/kg at $\leq 50\%$ of the original rate. If tolerated, the rate may be increased back to the original rate stated in the protocol.
Recurrent Grade 2	
• If the Grade 2 IRR recurred after reducing the dose to 1 mg/kg and the signs and symptoms are severe, permanently discontinue SL-172154
Grade 3	
• Immediately discontinue infusion of SL-172154• Vital signs should be measured after the onset of an IRR approximately every 15 minutes for one hour after discontinuation of SL-172154 infusion and then approximately every 30 minutes for hours 2 and 3 after the discontinuation of the SL-172154 infusion.• Begin IV infusion of normal saline and treat symptoms as indicated and per institutional guidelines e.g., epinephrine, bronchodilators, diphenhydramine, famotidine or other available H2 receptor antagonist, corticosteroids, consider opioids (e.g., meperidine) for rigors, oxygen, fluids, vasopressors, etc. Epinephrine is the drug of choice in an anaphylactic reaction and its administration should not be delayed.• Monitor subjects with close observation in an outpatient or inpatient setting for 12 hours or until recovery from symptoms. Strongly consider admission to hospital.• Rechallenge should not be attempted in cases of true anaphylaxis. In other cases, once the subject has completely recovered, carefully consider if it is safe for the subject to receive SL-172154 at the next scheduled dose with premedication and dose reduction.
◦ Reduce the SL-172154 dose for the next two infusions to 1 mg/kg at $\leq 50\%$ of the rate stated in the protocol. These two subsequent infusions of SL-172154 (after an event of Grade 3 event of IRR) must be administered in an inpatient or outpatient setting with prolonged observation for a minimum of 12 hours after the completion of the infusion.◦ If symptoms do not recur at 1 mg/kg SL-172154 dose, subsequent infusions may be administered at the original rate stated in the protocol. If no further symptoms, the SL-172154 dose may be re-escalated to 3 mg/kg but administered at $\leq 50\%$ of the rate stated in the protocol.
Recurrent Grade 3	
• If the Grade 3 IRR recurred, permanently discontinue SL-172154

General Guidance for Infusion-Related Reactions (IRRs) [Rosello, 2017a]

Grade 4

- Permanently discontinue SL-172154.
- Admit to hospital for close observation until resolution of symptoms.
- Vital signs should be measured after the onset of an IRR approximately every 15 minutes for one hour after discontinuation of SL-172154 infusion and then approximately every 30 minutes for hours 2 and 3 after the completion of the SL-172154 infusion.
- Manage severe IRRs per institutional standards (e.g., epinephrine, diphenhydramine, famotidine or other available H2 receptor antagonist, corticosteroids, consider opioids (e.g., meperidine) for rigors, bronchodilators, oxygen, fluids etc.). Epinephrine is the drug of choice in an anaphylactic reaction and its administration should not be delayed.

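### The fixed 1 and 3 mg/kg doses in the infusion-reaction guidance (Protocol 3.7.1.1) fit only subjects assigned 3.0 mg/kg; they conflict with Table 3 at 6.0 mg/kg and leave gaps in the recurrent Grade 2 stopping rule.

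*Protocol*

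**What the plan says.** The current protocol keeps three SL-172154 dose levels, 1.0, 3.0 and 6.0 mg/kg, in both regimens (Tables 1 and 2, Section 5.1.1), and each has a row in Table 3.

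Section 3.7.1 sets the general rule for related adverse events: "Only one level dose reduction is permitted for AE management and then SL-172154 administration should be held". Table 3 maps 6.0 to 3.0 mg/kg and 3.0 to 1.0 mg/kg. A subject at 1.0 mg/kg is interrupted and then restarted at the same dose or discontinued. A related event that "requires a dose hold of more than 28 days will result in permanent discontinuation of SL-172154". No exception is made for IRRs.

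Section 3.7.1.1 names doses instead of levels:

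- Grade 2 with severe symptoms: "the investigator may reduce the SL-172154 dose for the next two infusions to 1 mg/kg". If symptoms do not return, "SL-172154 dose may be increased back to 3 mg/kg".
- For a Grade 2 reaction that comes back: "If the Grade 2 IRR recurred after reducing the dose to 1 mg/kg and the signs and symptoms are severe, permanently discontinue SL-172154".
- After a Grade 3 reaction, if rechallenged: "Reduce the SL-172154 dose for the next two infusions to 1 mg/kg", after which "the SL-172154 dose may be re-escalated to 3 mg/kg".
- Recurrent Grade 3: "If the Grade 3 IRR recurred, permanently discontinue SL-172154". This rule and the Grade 4 rule carry no dose condition.

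**The concern.** The IRR text works for a subject assigned 3.0 mg/kg. At 6.0 mg/kg, two sites following the protocol could give 1 or 3.0 mg/kg after the same reaction. They could then stop, or only hold, after the same severe Grade 2 recurrence. At 1.0 mg/kg the recurrence rule cannot be triggered, because no reduction to 1 mg/kg can take place, and the literal return dose is above the assigned one.

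IRR is the most frequent adverse event with SL-172154 monotherapy (17 of 26 subjects, 65%), so this is the guidance most likely to be used. Section 3.5 also counts an adverse event requiring permanent discontinuation of SL-172154 as a DLT, so the choice of text could in principle decide whether a Grade 2 event enters the escalation count.

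**Working it through.** **Step 1: the two texts side by side**

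| Assigned dose | Section 3.7.1 and Table 3 | Section 3.7.1.1 | Return dose in 3.7.1.1 | Recurrent severe Grade 2 stop reachable? |
|---|---|---|---|---|
| 6.0 mg/kg | 3.0 mg/kg, one level, 3/6 = 50% of assigned | 1 mg/kg, two levels, 1/6 = 17% of assigned | 3 mg/kg; no stated route to 6.0 | Only if the site chose 1 mg/kg |
| 3.0 mg/kg | 1.0 mg/kg, 1/3 = 33% | 1 mg/kg, 33% | 3 mg/kg, the assigned dose | Yes, once reduced |
| 1.0 mg/kg | No reduction; interrupt, then restart or discontinue | 1 mg/kg, no change | 3 mg/kg, above assigned | No |

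At 6.0 mg/kg the two reduced doses differ threefold (3.0/1.0). The texts agree fully only in the 3.0 mg/kg row.

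**Step 2: the 6.0 mg/kg subject reduced to 3.0 mg/kg.** A second severe Grade 2 IRR does not meet the recurrence rule. Section 3.7.1 then says hold. Permanent discontinuation follows only if the hold passes 28 days, or if the event is judged an unacceptable risk under Section 3.11.

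**Step 3: how many escalation subjects could be at 6.0 mg/kg.** The plan has 12 escalation subjects per regimen (Section 3.1.1). Each regimen starts at 3.0 mg/kg and normally needs at least 3 evaluable subjects before a decision (Section 9.1.1). So at most about 12 − 3 = 9 per regimen, or 2 × 9 = 18 in all.

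**Step 4: expected Grade 3 IRRs.** In monotherapy, 1 of 26 subjects had a related Grade 3 IRR (Section 1.7.1): 1/26 = 3.8%, exact 95% CI 0.1% to 19.6%.

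- Expected number in 18 subjects: 18 × 1/26 = 0.69. The CI limits give 18 × 0.001 = 0.02 to 18 × 0.196 = 3.5.
- Using only monotherapy subjects at 3.0 mg/kg or above (2 + 6 + 5 = 13, Section 1.4.7): 18 × 1/13 = 1.4.
- If nobody receives 6.0 mg/kg, the number is 0. If both expansion cohorts used it (20 + 70 = 90 subjects), it is 90 × 1/26 = 3.5; the documents do not say that they will.

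These counts describe the Grade 3 dose conflict. They do not measure recurrent severe Grade 2 IRR, for which the documents give no frequency.

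**Step 5: the DLT route.** A related Grade 3 IRR is already a DLT, since the exceptions in Section 3.5 do not include IRR. Only the Grade 2 branch can change the count. It needs all of the following in one subject:

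1. a severe-symptom Grade 2 IRR on Cycle 1 Day 8;
2. the optional reduction;
3. a severe recurrence on Day 15, inside the 21- or 28-day window.

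If the Day 15 dose was 1 mg/kg, discontinuation is required and the event is a DLT. If it was 3.0 mg/kg, the event is not automatically a DLT. For this to turn the Table 12 decision from stay (1 of 3) to de-escalate (2 of 3), another of the three subjects must already have had a DLT.

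**The case against.** The best defence is that the specific rule overrides the general one. Section 3.7.1 calls itself general guidance. Section 3.7.1.1 deals only with IRRs and sets a temporary step of two infusions, which Table 3 does not have. Elsewhere, as for CRS, hepatotoxicity and thrombocytopenia, the protocol writes reductions as one dose level lower, so naming a dose could be deliberate. Section 3.7 adds that the guidelines are not prescriptive and refers sites needing guidance to the Medical Monitor. Variation after a severe Grade 2 IRR is also built in at every dose, because the reduction is optional.

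Part of this stands. It limits the consequences, and a sensible investigator would probably not raise a 1.0 mg/kg subject to 3 mg/kg. It does not settle the default. No sentence states the override, and the override would leave no route back to 6.0 mg/kg. The option in Section 3.7.1 to be more conservative is explained as interruption instead of reduction, not as a two-level cut. The amendment rationale (Sections 16.9 and 16.10), used here only as context, describes a step from 3 to 1 mg/kg and treats 3 mg/kg as the starting dose. That points to text written with 3.0 mg/kg subjects in mind.

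A reader might also infer a material distortion of the MTD. The documents do not support that: the sequence in Step 5 is narrow, and Section 3.5 lets the investigator and the SMC call other toxicities DLTs, so a severe recurrence can count under either text.

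**Conclusion.** The inconsistency is real in the operative text. At 6.0 mg/kg the protocol gives two reduced doses and does not say which governs. The recurrent severe Grade 2 stop misses a 6.0 mg/kg subject reduced under Table 3 and every 1.0 mg/kg subject.

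The size is probably small. The figure of about 0.7 Grade 3 IRRs rests on 18 escalation subjects at 6.0 mg/kg and on the 1/26 rate carrying over. That rate may be too low, because IRR frequency rose with dose, or too high, because dexamethasone premedication was added later. More subjects would be affected if enrolment exceeded plan or if expansion used 6.0 mg/kg.

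Two stronger readings should be set aside. A reader might infer overexposure at 6.0 mg/kg, but both texts lower that dose. A reader might also infer that IRR stopping is generally unsound, but the Recurrent Grade 3 and Grade 4 rules have no dose condition and are unaffected. The point concerns inconsistent dosing and stopping.

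**What to change.** In Section 3.7.1.1:

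- Replace the fixed doses in the Grade 2 and Grade 3 rows with: 'one dose level lower per Table 3 (no reduction below 1.0 mg/kg); may return to no more than the assigned dose'.
- Reword the recurrent Grade 2 row as: 'recurred with severe signs and symptoms after dose reduction, or at 1.0 mg/kg: permanently discontinue'.
- If 1 mg/kg is intended for subjects assigned 6.0 mg/kg, say so as an explicit exception to the one-level rule in Section 3.7.1, and state the dose to which they may return.

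The cost is one or two sentences in an amendment. Sample size and analysis do not change.

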3.7.1.2 Management of Cytokine Release Syndrome

CRS will be graded using the ASTCT Consensus Grading Criteria for CRS ([Table 4](#)).

Table 4 ASTCT Consensus Grading Criteria for CRS [[Lee, 2019](#)]

CRS Parameter	Grade 1	Grade 2	Grade 3	Grade 4
Fever ¹	Temperature $\geq 38^{\circ}\text{C}$	Temperature $\geq 38^{\circ}\text{C}$	Temperature $\geq 38^{\circ}\text{C}$	Temperature $\geq 38^{\circ}\text{C}$
		With		
Hypotension	None	Not requiring vasopressors	Requiring a vasopressor with or without vasopressin	Requiring multiple vasopressor (excluding vasopressin)
		And/Or²		
Hypoxia	None	Requiring low-flow nasal cannula ³ or blow-by	Requiring low-flow nasal cannula ³ , facemask, nonrebreather mask, or Venturi mask	Requiring positive pressure (e.g., CPAP, BiPAP, intubation and mechanical ventilation)

Abbreviations: ASTCT = American Society for Transplantation and Cellular Therapy; CPAP = continuous positive airway pressure; BiPAP = bilevel positive airway pressure
Organ toxicities associated with CRS may be graded according to CTCAE v5.0 but they do not influence CRS grading.

1. Fever is defined as temperature $\geq 38^{\circ}\text{C}$ not attributable to any other cause. In subjects who have CRS and receive antipyretic or anti-cytokine therapy, such as tocilizumab or steroids, fever is no longer required to grade subsequent CRS severity. In this case, CRS grading is driven by hypotension and/or hypoxia.
2. CRS grade is determined by the more severe event: hypotension or hypoxia not attributable to any other cause. For example, a patient with temperature of 39.5°C , hypotension requiring 1 vasopressor, and hypoxia requiring low-flow nasal cannula is classified as Grade 3 CRS.
3. Low-flow nasal cannula is defined as oxygen delivered at ≤ 6 L/minute. Low flow also includes blow-by oxygen delivery, sometimes used in pediatrics. High-flow nasal cannula is defined as oxygen delivered at > 6 L/minute.

General Guidance for Cytokine Release Syndrome (CRS) [Lee, 2014; Lee, 2019; BREYANZI® USPI, 2021; Porter, 2018]

Cytokine release syndrome (CRS) is a non-antigen specific, systemic inflammatory response that occurs as result of high-level immune activation with concomitant elevations of cytokines (e.g., IL-6, IL-10, TNF- α , IL-2, interferon gamma [β IFN γ]). CRS can be fatal or have life-threatening reactions. Evaluate for and treat other causes of fever, hypoxia, and hypotension. Determine CRS grade per the ASTCT Consensus Grading criteria for CRS in [Table 4](#) and manage CRS according to this guidance or per institutional guidance. NOTE: CRS may have a similar presentation to a type 1 HSR and may be clinically indistinguishable. Ensure that 2 doses of tocilizumab are available prior to infusion of SL-172154. When tocilizumab is not available, consider using a drug with similar mechanism of action such as anti-IL-6 receptor monoclonal antibodies (e.g., sarilumab) or anti-IL-6 mAbs (e.g., siltuximab). If CRS events occur, ad hoc labs should be collected as noted in Section [6.5.9.1](#).

Severity (ASTCT CRS Consensus Grading)	Management
Any Grade	
 Permanently discontinue SL-172154 if any grade CRS occurs at Cycle 1 Day 2 or later due to ADAs against SL-172154
Grade 1	
 Interrupt SL-172154 Vital signs should be measured approximately every 15 minutes for the first hour after discontinuation of SL-172154 infusion and then approximately every 30 minutes for the second hour. Monitor subjects with close observation in an outpatient or inpatient setting for 12 hours or until recovery from symptoms. Maintain IV access. Symptomatic treatment with antipyretic, antiemetics, analgesics, antihistamines (H1/H2 inhibitors) as needed; monitor fluid balance; assess for infection. Consider opioids (e.g., meperidine) for rigors. Regularly evaluate for signs of further deterioration 
Resume SL-172154 when all symptoms/ clinical features for CRS resolved, and follow the guidelines below:
 
 Subjects who have experienced grade 1 CRS should be hospitalized for the subsequent infusion of SL-172154; subjects should be under prolonged observation for a minimum of 12 hours after the completion of the infusion. For all subsequent infusions, infuse SL-172154 at the same dose level over at least twice the infusion time. If no recurrence of symptoms, subsequent infusions can be performed in an outpatient setting. Consider premedication (e.g., antipyretic, antihistamines) per institutional guidelines

General Guidance for Cytokine Release Syndrome (cont.)

Grade 2	
• Interrupt SL-172154• Vital signs should be measured approximately every 15 minutes for the first hour after discontinuation of SL-172154 infusion and then approximately every 30 minutes for the second hour.• Closely monitor cardiac and other organ function in an outpatient or inpatient setting for 12 hours or until recovery from symptoms. Consider admission to hospital for management of symptoms, evidence of organ dysfunction or administration of therapy.• Monitor subjects with continuous cardiac telemetry and pulse oximetry, closely monitor other organ functions.• Start IV infusion with normal saline. Administer oxygen if needed. Treat with antipyretic, H1/H2 antagonists (diphenhydramine, famotidine, or other available H2 receptor antagonist), and/or corticosteroids and manage per institutional guidelines.
○ If corticosteroids are initiated, continue corticosteroids for at least 3 doses or until complete resolution of symptoms, and consider corticosteroid taper.• Consider opioids (e.g., meperidine) for rigors.• Consider tocilizumab use for subjects with persistent signs and symptoms after interrupting SL-172154 and after corticosteroid treatment for CRS.
○ Administer tocilizumab as per your institutional guidelines and local prescribing information.• Subjects with extensive comorbidities or those of older age should be treated as for Grade 3. Subjects with worsening symptoms should be treated as for Grade 3. 
Resume SL-172154 at one dose level lower when all symptoms/ clinical features for CRS resolved and follow the guidelines below:
 
• Subjects who experience Grade 2 CRS should be hospitalized for the next two subsequent infusions of SL-172154. Subjects should be under prolonged observation for a minimum of 12 hours after the completion of the infusion.• For all subsequent infusions, infuse SL-172154 at least at twice the infusion time. If no recurrence of symptoms, subsequent infusions can be performed in an outpatient setting.• Premedicate with dexamethasone 20 mg, antipyretic, antihistamines (H1/H2 inhibitors), and manage per institutional guidelines.
---------	---------------------------------------------------------------------------------------------------------------------------------------------------------------------------------------------------------------------------------------------------------------------------------------------------------------------------------------------------------------------------------------------------------------------------------------------------------------------------------------------------------------------------------------------------------------------------------------------------------------------------------------------------------------------------------------------------------------------------------------------------------------------------------------------------------------------------------------------------------------------------------------------------------------------------------------------------------------------------------------------------------------------------------------------------------------------------------------------------------------------------------------------------------------------------------------------------------------------------------------------------------------------------------------------------------------------------------------------------------------------------------------------------------------------------------------------------------------------------------------------------------------------------------------------------------------------------------------------------------------------------------------------------------------------------------------------------------------------------------------------------------------------------------------------------------------------------------------------------------------------------------------------------------------------------------------------------------------------------------------------------------------------------------------------------------------------------------------------------------------------------------------------------------------------------------------------------------------------------------------------------------------------------------------------------------------------------------------------------------------------------------------------------------------------------------------------------------------------

General Guidance for Cytokine Release Syndrome (cont.)

Grade 3	
• Interrupt SL-172154
○ Permanently discontinue SL-172154 if CRS does not resolve within 72 hours with management.• Vital signs should be measured approximately every 15 minutes for the first hour after discontinuation of SL-172154 infusion and then approximately every 30 minutes for the second hour.• Hospitalization required for close monitoring and management of symptoms related to organ dysfunction.• Monitor subjects with continuous cardiac telemetry and pulse oximetry. Consider performing an ECHO/MUGA to assess cardiac function.• Treat hypotension with IV fluid for blood pressure support and/or pressers. Cryoprecipitate or fresh frozen plasma may be required for coagulopathy. Manage per institutional guidelines.• Implement additional management per institutional standards (e.g., epinephrine, diphenhydramine, famotidine or other available H2 receptor antagonist, corticosteroids, bronchodilators, oxygen, fluids, meperidine for rigors, etc.). Epinephrine is the drug of choice in an anaphylactic reaction and its administration should not be delayed.• Administer tocilizumab as per your institutional guidelines and local label.• Second-line therapies to be considered:
○ Methylprednisolone 2 mg/kg/day IV. If corticosteroids are initiated, continue corticosteroids for at least 3 doses or until complete resolution of symptoms, and consider corticosteroid taper. For subjects with severe neurologic symptoms, consider using dexamethasone due to more efficient penetration of the blood-brain barrier.○ anti-TNF-α mAbs (infliximab) or soluble TNF-α receptor (etanercept), or IL-1R-based inhibitors (anakinra). 
Resume SL-172154 at one dose level lower only when all symptoms/ clinical features of CRS resolve within 72 hours and follow the guidelines below:
 
• Subjects who experience Grade 3 CRS should be hospitalized for the next two subsequent infusions of SL-172154. Subjects should be under prolonged observation for a minimum of 12 hours after the completion of the infusion.• For all subsequent infusions, infuse SL-172154 at least at twice the infusion time. If no recurrence of symptoms, subsequent infusions can be performed in an outpatient setting.• Premedicate with dexamethasone 20 mg, antipyretic, antihistamines (H1/H2 inhibitors), and manage per institutional guidelines.• If Grade 3 CRS recurs, permanently discontinue SL-172154.
---------	------------------------------------------------------------------------------------------------------------------------------------------------------------------------------------------------------------------------------------------------------------------------------------------------------------------------------------------------------------------------------------------------------------------------------------------------------------------------------------------------------------------------------------------------------------------------------------------------------------------------------------------------------------------------------------------------------------------------------------------------------------------------------------------------------------------------------------------------------------------------------------------------------------------------------------------------------------------------------------------------------------------------------------------------------------------------------------------------------------------------------------------------------------------------------------------------------------------------------------------------------------------------------------------------------------------------------------------------------------------------------------------------------------------------------------------------------------------------------------------------------------------------------------------------------------------------------------------------------------------------------------------------------------------------------------------------------------------------------------------------------------------------------------------------------------------------------------------------------------------------------------------------------------------------------------------------------------------------------------------------------------------------------------------------------------------------------------------------------------------------------------------------------------------------------------------------------------------------------------------------------------------------------------------------------------------------------------------------------------------------------------------------------------------------------------------------------------------------------------------------------------------------------------------------------------------------------------------------------------------------------------------------------------------------------------------------------------------------------------------------------------------------------------------------------

General Guidance for Cytokine Release Syndrome (cont.)

Grade 4	
• Permanently discontinue SL-172154.• Hospitalization required for close monitoring and management of symptoms related to organ dysfunction.• Vital signs should be measured approximately every 15 minutes for the first hour after discontinuation of SL-172154 infusion and then approximately every 30 minutes for the second and third hours.• Consider intensive-care supportive therapy• Monitor subjects with continuous cardiac telemetry and pulse oximetry• Consider performing an ECHO/MUGA to assess cardiac function.• Treat hypotension with IV fluid for blood pressure support and/or pressers. Administer oxygen for treatment of hypoxia. Cryoprecipitate or fresh frozen plasma may be required for coagulopathy. Manage per institutional guidelines.• Implement additional management per institutional standards (e.g., epinephrine, diphenhydramine, famotidine or other available H2 receptor antagonist, corticosteroids, bronchodilators, oxygen, fluids, meperidine for rigors, etc.). Epinephrine is the drug of choice in an anaphylactic reaction and its administration should not be delayed• Administer tocilizumab as per your institutional guidelines and local prescribing information.• Second-line therapies to be considered:
○ Methylprednisolone 2 mg/kg/day IV. If corticosteroids are initiated, continue corticosteroids for at least 3 doses or until complete resolution of symptoms, and consider corticosteroid taper. For subjects with severe neurologic symptoms, consider using dexamethasone due to more efficient penetration of the blood-brain barrier.○ anti-TNF-α mAbs (infliximab) or soluble TNF-α receptor (etanercept), or IL-1R-based inhibitors (anakinra).
---------	------------------------------------------------------------------------------------------------------------------------------------------------------------------------------------------------------------------------------------------------------------------------------------------------------------------------------------------------------------------------------------------------------------------------------------------------------------------------------------------------------------------------------------------------------------------------------------------------------------------------------------------------------------------------------------------------------------------------------------------------------------------------------------------------------------------------------------------------------------------------------------------------------------------------------------------------------------------------------------------------------------------------------------------------------------------------------------------------------------------------------------------------------------------------------------------------------------------------------------------------------------------------------------------------------------------------------------------------------------------------------------------------------------------------------------------------------------------------------------------------------------------------------------------------------------------------------------------------------------------------------------------------------------------------------------------------------------------------------------------------------------------------------------------------------------------------------------------------------------------------------------------------------------------------------------------------------------

